Overview of study design. This is a prospective, observational cohort study to examine the comparative effectiveness of short *versus* prolonged treatment of neonatal seizures due to an acute symptomatic cause. To permit causal inference with an observational study design, we will use a propensity score analysis approach. This will account for baseline patient characteristics that influence treatment duration recommendations. For infants with comparable propensity scores, the distribution of observed baseline covariates will be similar between the treatment groups.^{22,23}

Newborns and their families will be enrolled at the seven tertiary children's hospitals that make up the *Neonatal Seizure Registry*. Preliminary

data from the *Neonatal Seizure Registry* indicate that there is substantial heterogeneity in treatment, such that some neonates with acute symptomatic seizures are treated for a short duration (seizure medication discontinued prior to discharge home) and some neonates are treated for prolonged duration (medication continued until follow up evaluation at 2-4 months of age or longer), and that this is largely independent of the seizure etiology and severity and most related to study center (p<0.001). Through this proposal, we will obtain consent to study outcomes for 150 infants already enrolled in the *Neonatal Seizure Registry* who are still young enough to permit prospective 24-month outcome assessment, and will prospectively enroll an additional 150 newborns with acute symptomatic neonatal seizures. These infants will be enrolled prior to discharge from hospital and evaluated with EEG at age 2-4 months and by telephone and follow-up questionnaires at age 12, 18, and 24months. Validated parent and family well-being instruments will be administered at the time of hospital discharge and again at 12-month, 18-month, and 24-month follow-ups (**Figure 1**).

The study team is uniquely qualified to conduct cutting-edge comparative effectiveness research for

neonatal seizures. The co-PIs are highly respected neonatal neurologists with active research programs that are directly relevant to the present proposal and a track record of high quality multidisciplinary research. They have enlisted experienced parent partners and stakeholder collaborators who have both personal and professional experience with research and with neonatal seizures. The team of co-investigators completes this

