"[Y]our proposal of a comparative effectiveness study is currently the best opportunity to gain robust data regarding this important question... We anticipate that the data generated through this ground-breaking research could lead to a change in clinical practice." - American Academy of Pediatrics, Section on Neurology Letter of Support

multidisciplinary team, to insure that the work proposed is conducted with the highest level of patientcenteredness, robust study design, and valid statistical analyses.

Subject identification, selection and recruitment [PC-2]. Study personnel at each site will review daily admissions to the Intensive Care Nursery, Pediatric and Cardiac Intensive Care Units, as well as records of patients monitored with long-term EEG, to identify eligible infants. Neonatal seizures affect newborns of both genders and all races and ethnicities. Therefore, no patient will be excluded on the basis of gender, race or ethnicity. A study investigator will contact the parents/legal guardians of eligible patients and, using a consent form approved by the local Institutional Review Board, describe the known risks and benefits of the study. The consent teams will include only experienced study personnel who are sensitive to the vulnerable nature of this population and who will emphasize the voluntary nature of research. All site PIs have extensive experience with patient recruitment for clinical trials and cohort studies. *We expect high rates of enrolment based on feedback from our Parent Partners regarding the importance of the question and the low risk observational nature of the study*. A representative sample of 150previously enrolled infants who are young enough allow for

PCORI Research Plan version 2 8/1/2016

prospective 24-month follow-up assessments will be contacted by the study sites to request consent for participation in this study. Once a family agrees to participate, study personnel will begin data collection. For prospectively enrolled infants, plans for follow-up appointments will be initiated prior to the family's discharge home from the hospital. Infants at each site are eligible for clinical follow up as outpatients through their respective Pediatric Neurology Clinics and High-Risk Newborn Follow-up Programs, which will help with participant retention.

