Patient Evaluation						
- Follow-up EEG (age 2-4 months) (Aim 1)		✓	\checkmark	\checkmark	\checkmark	
- 24-month follow up (Aim 1) - previous NSR subjects		\checkmark	✓	\checkmark		
- 24-month follow up (Aims 1&3) - newly enrolled subjects			\checkmark	\checkmark	\checkmark	\checkmark
Analysis						
- Interim analysis				\checkmark	✓	
- Final analysis						\checkmark
Progress reports						
- Interim progress reports	\checkmark	\checkmark	✓	\checkmark	\checkmark	
- Final progress report						\checkmark
Engagement Updates	✓	✓	✓	✓	✓	~
Dissemination						
- Write manuscripts					✓	\checkmark
 Submit copies of published manuscripts 					\checkmark	\checkmark
 Presentations by PIs/stakeholders at national meetings 					✓	\checkmark
- Write management guidelines						\checkmark
- Apply for additional funding					✓	\checkmark
- Newsletters to participating families to report results					✓	\checkmark
- Partner with Hand to Hold to disseminate results online					✓	\checkmark

E. Patient Population

Table 4: Quarterly Neonatal Seizure Registry enrollment (6/2013 to 9/2015)			
Site	Median (min, max)	Total Newborns Enrolled in NSR	
UCSF	6 (2, 13)	59	
University of Michigan	12 (5, 16)	102	
MGH	3 (0, 10)	29	

Recruitment Plan. We aim to collect follow-up information for 150 infants that have already been enrolled in the *Neonatal Seizure Registry* (from among >300 eligible newborns; a representative sample of the youngest infants at the time of study initiation will be approached for consent, to allow for prospective collection of 24-

Stanford	6 (0 , 29)	72
СИМС	10 (0, 37)	86
СНВ	11 (5, 17)	79
СНОР	2 (0, 19)	40

month outcome data). An additional prospective sample of 150 newborns will also be enrolled. We have had stable enrollment of 20-30 newborns/month, >70% of whom have acute symptomatic seizures and would meet enrollment criteria for the proposed study. Thus, we expect 250-375 eligible infants over the 18 month enrollment period. We, therefore, will need to enroll 40-60% of eligible newborns, which is very conservative for a non-intervention study with non-invasive follow-up. We will monitor enrollment monthly and address lagging rates on a site-specific basis, as necessary. Given that PCORI requests data within nine months of the end of the final year of funding, even if recruitment is slower than anticipated, there is an additional six months of recruitment time available to us to meet this deadline.

Table 5: Recruitment Goals

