	Previously-enrolled	Prospectively-
	infants	enrolled newborns
Total number of study participants expected to be screened:	300	375
Total number of study participants expected to be eligible of	300	300
those screened:		
Target sample size (use same number stated in milestones):	150	150

Race	Male (N) 55%	Female (N) 45%	Total (N)
American Indian/Alaska Native	1	0	1
Asian	10	8	18
Black/African-American	21	17	38
Hawaiian/Pacific Islander	1	0	1
White	88	73	161
Multirace	7	6	13
Ethnicity	Male (N)	Female (N)	Total (N)
Hispanic (Latino/Latina)	25	21	46
Non-Hispanic	112	92	204

 Table 6: Estimated Final Racial/Ethnic and Gender Enrollment Table [RQ-3]

The study population will be newborns with seizures who are admitted at one of the participating children's hospitals, and their parents. Study sites were selected based on their enrollment of patients in the *Neonatal Seizure Registry* and their ability to confirm neonatal seizure diagnoses with video EEG monitoring, according to the American Clinical Neurophysiology Society (ACNS) guidelines³⁷.

Inclusion criteria [RQ-3]

- Neonates <44 weeks postmenstrual age at seizure onset
- Seizures due to an acute symptomatic cause (including, but not limited to hypoxic ischemic encephalopathy, stroke, or cerebral hemorrhage)
- Parent(s) who are English or Spanish literate (with assistance of interpreter)

Exclusion criteria

- Neonates at risk for adverse outcome *independent of* seizures and underlying brain injury (including but not limited to: inborn errors of metabolism, fetal infection, brain malformation, or genetic syndrome)
- Neonates with transient cause for seizures (e.g., mild hypoglycemia, hyponatremia, hypocalcemia)
- Newborns with neonatal-onset epilepsy syndromes

- Neonates who do not survive the initial hospital admission
- Neonates will not be excluded based on race, ethnicity, gender or gestational age

Study population [RQ-3]. We will recruit 300 newborn infants with acute symptomatic seizures (including 150 who were previously enrolled in the *Neonatal Seizure Registry*). No infant will be excluded based on gender, race, or ethnicity. Neonates with seizures are often critically ill, and some do not survive their initial hospital admission (16% in-hospital mortality in the *Neonatal Seizure Registry*). We will only enroll newborns who survive to hospital discharge.

Inclusion of Women & Minorities.

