Consistent Data Collection: We will use the existing data dictionary for the *Neonatal Seizure Registry*, which is based on recent literature review and widely used definitions. Standard instructions and definitions are included in the Manual of Operations.

Systematic Patient Enrollment and Follow-up: Every infant diagnosed with neonatal seizures at the participating centers will be a potential candidate for enrollment. Only families whose infants survive to hospital discharge will be approached for consent (~16% in-hospital acute mortality among those already enrolled in the *Neonatal Seizure Registry*). This will avoid selection bias and allow for the most widely applicable data set. Each site will maintain a log of families who decline to consent for this study. The log will include gender, race/ethnicity, and the reason for the neonatal seizures (these data are already gathered through the *Neonatal Seizure Registry*). This will allow for prospective identification of any biases in enrollment, so that changes in the consent process may be implemented as needed to enhance generalizability of the study sample.

Procedures to Monitor and Minimize Loss to Follow-up: Quarterly enrollment and follow-up reports will be generated for each site, so that the follow-up rates are clear and any center for which the target appears to be in jeopardy can be readily identified before the follow-up target is missed. The target is >85% follow-up for the 24-month assessments. We will prospectively determine the actions to be employed in the event that this target is in jeopardy. At the outset of the study, we will develop a patient retention plan that documents when a patient will be considered lost to follow-up and what actions will be taken to minimize such loss.

- At the time of enrollment, the following data will be collected: Telephone, mailing address, and email address for the neonate's parent/legal guardian, as well as alternate contact information for that parent/guardian (e.g. a grandparent or close friend's contact information, with that person's permission).
- The 2-4 month follow-up EEG will be planned and scheduled at the time of study enrollment, with every effort made to coordinate that appointment with another clinically-indicated appointment (*e.g.*, the pediatric neurology follow-up clinic visit). This will minimize travel for infant and family and should enhance retention.

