- The family will be given a reminder telephone call several days before the 2-4 month visit.
- Contact information will be verified and updated when the family comes to the 2-4 month EEG.
- If a family misses the 2-4 month EEG, then they will be contacted via telephone call within 3 days of the missed appointment. If there is no response, then an email will be sent after 5-7 days and/or a telephone call will be placed to the alternate phone number. The EEG will be rescheduled if at all possible.
- When the infant reaches 11 months, a letter will be mailed and/or emailed to the family, to remind them of the 12month telephone assessment. Families will be asked to contact the study coordinator to arrange a mutually convenient time for the 12-month telephone interview. If the family does not reply, the study coordinator will contact them via telephone and/or email to confirm an appointment for the follow-up assessment.
- In the event that an enrolled infant dies, the site's electronic medical record will be updated per local protocol. Many of the sites utilize an electronic medical record that automatically notifies a study team of a participant's death. The site study coordinators will verify that the patient is listed as living prior to extending an invitation for follow-up. If the patient is listed as deceased, the family will not be contacted.
- If a family withdraws from the study, the coordinators will attempt to document the reason for withdrawal so that issues can be identified and addressed.

Data Collection to Address Confounding: We will prospectively collect data for potential confounders to allow for the planned propensity scoring analysis, including:

- Term versus preterm at birth
- Confirmation of electrographic seizures versus diagnosis on clinical grounds alone
- Severity of seizures
- Etiology of seizures
- Number of seizure medications during the inpatient hospitalization
- Highest recorded phenobarbital level
- Abnormal neurological examination (consciousness, tone, or reflexes) at the time of discharge
- NICU length of stay
- Institution

Robust Analysis of Confounding Factors [DR-3]: Our plans to address analysis of confounding factors are addressed in the application's data analysis plan sections (see pages 9-12).

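### Half the Aim 1 sample is recruited after the neonatal admission and half before discharge, yet the halves are pooled and no planned analysis includes cohort or enrolment period

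*Combined protocol and SAP*

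**What the plan says.** **Registry half.** The Overview of study design takes 150 infants already in the Neonatal Seizure Registry "who are still young enough to permit prospective 24-month outcome assessment". Under Subject identification, selection and recruitment, these families "will be contacted by the study sites to request consent for participation in this study". The Recruitment Plan in section E adds that "a representative sample of the youngest infants at the time of study initiation will be approached for consent".

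**New half.** The Overview says of the 150 new infants: "These infants will be enrolled prior to discharge from hospital".

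**Eligibility.** The survival condition for the whole study is survival to hospital discharge. The Exclusion criteria include neonatal-onset epilepsy syndromes and conditions such as "inborn errors of metabolism, fetal infection, brain malformation, or genetic syndrome". They give no date by which such a diagnosis must be known.

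**Analysis.** Aim 1 treats the 300 as one sample. The nine propensity covariates under Statistical analysis and addressing causal inference, and the parallel list in Appendix 6 (Data Collection to Address Confounding), contain neither cohort nor enrolment period. Nor do Potential participant subgroups, the instrumental-variable analysis under Sensitivity analyses, or the loss-to-follow-up and imputation analyses under Missing data.

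**Selection.** Appendix 6 (Systematic Patient Enrollment and Follow-up) says of approaching only families of survivors to discharge: "This will avoid selection bias and allow for the most widely applicable data set". Of the families who decline, it says: "The log will include gender, race/ethnicity, and the reason for the neonatal seizures".

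**The concern.** The two halves enter at different points in the child's course. A family approached in hospital decides without knowing how the child will develop. A registry family decides months later, when delay or seizures may already have appeared.

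Appendix 6 (Possible biases due to differential loss to follow-up) accepts that infants discharged without medication may be lost more often, and that distant families of children who are doing well may return less. In the registry half the same forces can act at consent, before the child is a participant. The planned comparison of lost and retained children, and the imputation, cover participants only, so neither can see this. The decline log does not record discharge medication.

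Separately, the halves come from different calendar periods. If stopping practice and outcome both changed over time, cohort would confound the pooled comparison. Institution as a covariate or instrument addresses site, not period and not consent that depends on child status. At stake is how far a pooled non-inferiority result, intended to support practice guidelines, can be taken at face value.

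**Working it through.** **1. The plan's own figure.** Inputs from Sample Size Calculations, Aim 1a: margin 7 points, SD 16.5 (12 months), true difference 0, one-sided 5%, 80% power, stated N = 192. With short-arm share p, total N = [1/(p(1−p))] × [16.5 × (1.645 + 0.842)/7]².
- Registry split 23:77: N = 194.0.
- Planned split 30:70 (90:210): N = 163.6, and 163.6/0.85 = 192.4 after 15% loss.

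The allocation behind 192 is not stated and either route fits. No stated figure is shown to be wrong.

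**2. Age at approach.** Stable enrolment is 20–30 a month with at least 70% eligible, so 14–21 eligible a month. The youngest 300 then span 300/21 to 300/14, or about 14 to 21 months of births. An age near two years is an upper bound, not a stated figure.

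**3. Bias from omitting cohort (assumed inputs).** Bias = (difference between arms in cohort share) × (difference between cohorts in mean WIDEA). The documents give neither term. With assumed differences of 10–30 points in share and 2–10 WIDEA points:
- smallest: 0.10 × 2 = 0.2 points (3% of 7);
- largest: 0.30 × 10 = 3.0 points (43% of 7);
- equal share in both arms: 0.

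**4. Bias from selective consent (assumed inputs, secondary endpoint).** Take true epilepsy incidence of 20%. Let prolonged-arm registry families consent at 60% if the child has epilepsy and 40% if not, and short-arm families at 50% regardless. Observed prolonged-arm incidence in that half is 0.2×0.6/(0.2×0.6 + 0.8×0.4) = 0.12/0.44 = 27.3%. The bias of 7.3 points is about 3.6 when pooled with an unbiased half, 28% of the 13-point margin. Swapping the rates gives 0.08/0.56 = 14.3%, a bias of 5.7 points the other way.

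**5. Would the medication split reveal case 4?** Only weakly. Overall consent is 44% (prolonged) and 50% (short). From 23:77, the short share among consenters becomes 0.23×0.50/(0.23×0.50 + 0.77×0.44) = 0.115/0.454 = 25%. With 231 and 69 families approached, the 6-point consent gap has standard error √(0.44×0.56/231 + 0.50×0.50/69) = 6.8 points.

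**6. Cost of a cohort term.** Variance inflation = 1/(1 − d²·p(1−p)/[q(1−q)]), with p = 0.30, q = 0.50 and d the difference in cohort share. For d = 0.10, 0.20 and 0.30 it is 1.01, 1.03 and 1.08. The pooled analysis keeps 89–91% power at margin 7 with 15–20% loss and the plan's 9% inflation.

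**7. Precision by cohort.** One cohort is 45:105 before loss. SE = 16.5 × √(1/n₁ + 1/n₂); power = Φ(7/SE − 1.645).

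| Loss | n₁ : n₂ | SE | Power | Power with 9% inflation |
|---|---|---|---|---|
| 15% | 38.25 : 89.25 | 3.19 | 71% | 68% |
| 20% | 36 : 84 | 3.29 | 69% | 65% |

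The difference between the two cohort effects has SE √2 × 3.19 = 4.51 to √2 × 3.29 = 4.65. Its 95% interval is therefore about ±8.8 to ±9.1 points.

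**The case against.** Several stronger readings are tempting, and the documents do not support them.

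- **Registry children are excluded on later diagnoses.** Nothing says they are re-screened. Table 5 expects 300 eligible of 300 screened, and the registry is described as not structured for prospective neurodevelopmental follow-up. The criteria are worded for newborns, and the Manual of Operations, which was not available, may set a date. What stands is that the protocol gives no ascertainment date.
- **Parents already know the outcome.** The 24-month WIDEA lies ahead for every child. They know interim status. For epilepsy this matters more, because the Specific Aims place the highest risk in the first year.
- **Survival selection distorts the primary comparison.** The sentence "If the patient is listed as deceased, the family will not be contacted" governs follow-up of enrolled infants and is not a registry recruitment rule. The primary analysis is complete-case, so a 24-month WIDEA requires survival in both halves. What stands is that deaths between discharge and contact would go uncounted in one half.
- **The registry half alone could produce the non-inferiority result.** This is not shown. The documents give no consent rates by arm and outcome and show no shift in stopping practice over time, and the illustrated bias can take either sign.

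It is also fair to say that participation by arm is not wholly hidden. The registry's discharge-medication split is already known (23:77 among 306) and can be compared with that of consenters. Finally, a cohort covariate does not correct outcome-dependent consent within the registry half. That is right and limits what the fix can claim.

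**Conclusion.** The point holds as an omission in the planned analysis, not as a demonstrated bias. The halves are recruited under different conditions and pooled for Aim 1, and no planned analysis compares them or adjusts for cohort or period. The assurance that selection bias is avoided is therefore unsupported for the registry half.

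The size is unknown. It is zero if neither selection nor cohort share differs by arm. The 0.2 to 3.0 WIDEA points and the 3.6 epilepsy points rest on assumed inputs and only show what is possible. The power figures assume the 12-month SD of 16.5, the 7-point margin, an even cohort split and 30:70 arms in each cohort. Hindsight exclusion remains a possibility only. The change is worth making because it is cheap and removes an avoidable question about the main result.

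**What to change.** 1. Add cohort (previously enrolled or new) to the propensity and outcome models for Aim 1.
2. As a sensitivity analysis, report the treatment effect in each cohort with a treatment-by-cohort interaction, and say whether the new-infant cohort points the same way. A non-significant interaction should not be read as agreement.
3. State that eligibility in both halves is judged only on information recorded up to initial discharge. Keep children with later genetic or epilepsy diagnoses in the primary analysis and exclude them only in a sensitivity analysis.
4. Compare the discharge-medication split among consenting registry infants with the registry's known split, preferably within site because the share stopping ranges from 3 to 75%. Add medication status to the decline log only if compatible with the rule in Appendix 6 (Data Safety and Security) that earlier registry data are used only after consent.
5. Report known post-discharge deaths by arm and cohort.
6. Remove or qualify the Appendix 6 statement on selection bias.

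**Cost:** protocol and analysis wording, one covariate, and variance inflation of about 1 to 8% under the assumed imbalances. Cohort-specific estimates will be imprecise. They can help to reveal outcome-dependent consent in the registry half but cannot remove it.

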Participants at the Patient and Family Research Council felt strongly that *"all of these are important outcomes."* [name], Parent Partner, re-iterated this point: *"the developmental outcome matters only in the context of epilepsy and quality of life outcomes; they are all related and all important."*

Data Analysis [IR-3]. The centers from the *Neonatal Seizure Registry* enrolled 306 consecutive newborns with seizures due to acute symptomatic cause, and who survived hospital discharge, over our initial 12-27 months of collaboration (variable timing of initiation of enrollment by site). We conservatively estimate that we can enroll 150 of these infants to collect personal health information and follow up data, as well as 150 additional newborns over the 18 months proposed, for a total of 300 subjects with outcome measures for all three aims. This will require that we enroll ~50% of eligible newborns, a very achievable recruitment goal for an observational study.

Sample Size Calculations

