Based on audits of our *Registry* data, we expect <1% missing data for the following key elements: institution, sex, ethnicity, gestational age at birth, delivery mode, Apgar scores, hypothermia treatment, indication for EEG, seizure type, primary seizure etiology, disposition and seizure medication prescribed at the time of discharge. For Aims 1 and 3, in our study design we have conservatively accounted for 15% loss to follow-up (the anticipated main source of missing data) and have adjusted our enrollment target accordingly. We will perform sensitivity analyses to assess the potential impact of loss to follow-up: we have extensive information about our participants and will compare those that are and are not lost to follow-up. We will compare our primary analysis (a complete case analysis) with an analysis using multiple imputation using the "multiple imputation with chained equations" methodology. This approach allows us to specify realistic models for each variable, such as the ordered categorical for the Engel scale. For Aim 2, we expect little to no missing data. Also, for Aim 3, we will audit the amount of missing data for the open-ended free-text questions to determine if there are patterns and will consult with our Parent Partners about ways to improve response rates if needed.

Heterogeneity of treatment effects [HT-1 to 4]. As suggested by PCORI methodological guidelines, all assessments of heterogeneity of the effect of short versus prolonged phenobarbital treatment have been preplanned and have been justified (see *Potential participant subgroups* section below). Analysis will be by entering subgroup by intervention interaction effects in the analyses described above to test for moderation.

Reporting plan [IR-6]. Data will be reported according to STROBE (Strengthening the Reporting of Observational studies in Epidemiology) guidelines, as is recommended for observational studies.

Patient-centered outcomes research (PCOR) data registry details are presented in Appendix 6.

D. Project Milestones and Timeline

Table 3: Project Timeline

	Months					
	1-6	7-12	13-18	19-24	25-30	31-36
Planning						
- Finalize protocol	\checkmark					
- IRB approval	\checkmark					
 Clinicaltrials.gov registration & results reporting 	~					\checkmark
Patient Enrollment						
- Start recruitment		\checkmark				
- Complete 25% recruitment		\checkmark				
- Complete 50% recruitment			✓			
- Complete 75% recruitment			✓			
- Complete enrollment				~		

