Neonatal seizures affect boys slightly more often than girls (*Neonatal Seizure Registry* data: 55% male, 45% female), but children of all races and ethnicities are affected. Among the *Neonatal Seizure Registry's* subjects, the distribution of race/ethnicity is similar to the American pediatric population. We anticipate a similar distribution for the proposed follow-up study, which will be representative of American children.

Inclusion of Children. All study subjects will be children.

Potential participant subgroups [RQ-4; HT-1 to 4].

Our study is powered to evaluate the primary outcome (development at 24 months) across a wide-ranging population of neonates with seizures. This will improve generalizability. We will also have an opportunity to perform exploratory secondary analyses for some subgroups:

- EEG confirmed vs. clinically diagnosed neonatal seizures: Although all *Neonatal Seizure Registry* sites conform to the ACNS Guidelines for neonatal EEG monitoring³⁸, there are occasions in which an at-risk infant's clinical events resolve prior to the initiation of EEG. In the proper clinical context, many such newborns are treated empirically with anticonvulsant medications. In two small studies, the risk for subsequent epilepsy was higher among infants with EEG-confirmed neonatal seizures than those with clinically diagnosed seizures^{3,39}. Therefore, we will evaluate for differences in 24-month outcomes between those with clinical versus EEG-confirmed seizures.

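### Table 3 places the final analysis up to a year before the last new infants can have the 24-month primary outcome, and the six spare recruitment months do not exist

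*Combined protocol and SAP*

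**What the plan says.** The subgroup section names the endpoint: "Our study is powered to evaluate the primary outcome (development at 24 months) across a wide-ranging population of neonates with seizures". The Data Analysis section counts 150 registry infants "as well as 150 additional newborns over the 18 months proposed, for a total of 300 subjects with outcome measures for all three aims". The overview of the design has the new infants enrolled before they leave hospital.

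Table 3 places "Start recruitment" and the 25% milestone in months 7-12, the 50% and 75% milestones in months 13-18, and "Complete enrollment" in months 19-24. The row "24-month follow up (Aims 1&3) - newly enrolled subjects" is ticked in months 13-18, 19-24, 25-30 and 31-36. The final analysis is ticked only in months 31-36. Appendix 6 refers to a three-year grant cycle and sets a target of more than 85% follow-up at 24 months.

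The Recruitment Plan gives an 18-month enrolment period ("Thus, we expect 250-375 eligible infants over the 18 month enrollment period"). It notes that the funder wants data within nine months of the end of funding, and concludes that if recruitment is slow "there is an additional six months of recruitment time available to us to meet this deadline".

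**The concern.** A newborn enrolled in month 7 or later cannot be 24 months old before about month 30 or 31, so the first three ticks in the 24-month row for new infants are essentially impossible. The last infant enrolled on schedule turns 24 months at about month 48, a year after the last month shown for the final analysis.

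The primary analysis is a complete-case analysis. If the timetable is followed, most of the new cohort would therefore be missing from it for purely calendar reasons. The power statement, the 4.25% margin quoted for 24 months and the Aim 3 detectable difference all assume a full cohort. The six-month sentence is the Recruitment Plan's fallback in calendar time for slow accrual, so the error also removes a safeguard that the plan believes it has.

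**Working it through.** **Inputs.** Recruitment in months 7-24 (Table 3, 18 months). Endpoint at age 24 months. Funding ends at month 36 (Appendix 6), so data are due by month 36 + 9 = 45 (Recruitment Plan). 150 registry infants, whose 24-month visits Table 3 places in months 7-24, plus 150 new infants. One-sided 5% test (Aim 1a).

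**1. The plan's own recruitment figures.** Eligible infants: 20 × 0.70 × 18 = 252 to 30 × 0.70 × 18 = 378, against 250-375 stated. Uptake needed: 150/375 = 40% to 150/250 = 60%, as stated. The 18-month window is therefore the one the plan works with.

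**2. The six spare months.** Last usable enrolment month = deadline − follow-up length. Slack = that month − 24.

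| Follow-up | Last enrolment for month 45 | Slack |
|---|---|---|
| 12 months | 33 | +9 |
| 18 months | 27 | +3 |
| 24 months | 21 | −3 |

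Six extra months fit only a 12-month endpoint (24 + 6 + 12 = 42, inside 45). With 24 months they would need 24 + 6 + 24 = month 54, nine months past the deadline.

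**3. New infants with a 24-month score at month D.** This is cumulative accrual at month D − 24.
- Month 36 (accrual to month 12): 25% by the milestones = 37.5 infants; (12 − 6)/18 = 33% if uniform = 50. With the registry infants, 187.5 to 200 of 300. The 50% milestone falls in months 13-18, so Table 3 alone permits anything up to just under 50%, or about 150 + 75 = 225.
- Month 45 (accrual to month 21): uniform 15/18 = 83% = 125; milestones, midway between 75% and 100%, 87.5% = 131. Total 275 to 281.
- Month 48: all 300.
- If every infant is already one month old at enrolment, the month-36 shares rise to 33-39% (200-208 in total).

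At month 36 the ceiling on 24-month follow-up across the cohort is 188/300 = 63% to 200/300 = 67%, or 225/300 = 75% on the widest reading. All are below the 85% target before anyone is lost.

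**4. Power for Aim 1a at the 4.25% margin.** The 24-month SD is not printed, so I assume 80% power at N=300 and scale, holding loss, the 9% inflation and the group split constant. SD and margin then cancel: power = Φ(2.487 × √(n/300) − 1.645), where 2.487 = 1.645 + 0.842.

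| n with 24-month data possible | Power |
|---|---|
| 187.5 (month 36, milestones) | Φ(0.32) = 63% |
| 200 (month 36, uniform) | Φ(0.39) = 65% |
| 225 (month 36, upper bound) | Φ(0.51) = 69% |
| 275 (month 45, uniform) | Φ(0.74) = 77% |
| 281 (month 45, milestones) | Φ(0.76) = 78% |

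**5. Aim 3.** The plan's figure reproduces: (1.96 + 0.842) × √(1/36 + 1/84) = 0.56. It needs 120 prospective families with discharge and 24-month data, which is 150 less 20%. At month 36 the same 20% dropout leaves 37.5 × 0.8 = 30 to 50 × 0.8 = 40 families. Split 30:70, that is 9:21 to 12:28, and the detectable difference is 2.80 × √(1/9 + 1/21) = 1.12 to 2.80 × √(1/12 + 1/28) = 0.97.

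**The case against.** The dates cannot be defended, but four arguments limit what follows from them.

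*Power at the margin of 7.* A reader might put the month-36 numbers into the plan's SD of 16.5 and conclude that the study is underpowered even at a margin of 7. The documents do not support this. Under Aim 1a, 16.5 is the 12-month SD, and the 24-month SD is said to be lower. If 4.25 points gives 80% power on 192-234 effective subjects split 30:70, the implied 24-month SD is about 11-12. Power at a margin of 7 would then be roughly 94-98% with 146-156 effective subjects. The 12-month score, to which 16.5 does apply, is reached by all 300 infants by month 24 + 12 = 36. This argument stands.

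*The month-45 deadline.* A lock at month 45 would lose only 6-8% of the cohort (275-281 of 300), not a third. This stands as arithmetic. However, the data-sharing section treats the nine months as time to prepare the final data set, so using all of it for follow-up leaves no time for cleaning or analysis.

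*The accrual range.* The 25-33% depends on how accrual runs within the Table 3 columns, and it is unclear whether the milestones count the 150 new infants or all 300. This stands, which is why the upper bound of just under 50% is shown. No reading comes near the full cohort.

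*No order to lock early.* Nothing in the text says to lock with visits outstanding. Appendix 6 makes the 24-month contact the last one and aims for more than 85% follow-up, so the intent is evidently to follow everyone. This also stands, but it sharpens the conflict with the scheduled final analysis.

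**Conclusion.** The timetable contradicts the 24-month endpoint and must be reconciled with it. At the scheduled analysis about 188-200 of 300 infants, and at most about 225, could have the primary outcome before loss to follow-up. On the scaling assumption above, power at the 4.25% margin is then about 63-65%, up to about 69%, instead of 80%. A month-45 lock recovers most of this (about 77-78%) but still not 300 infants. The six spare recruitment months do not exist for this endpoint; the plan is already about three months short.

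It would go too far to infer that the study cannot answer its question, or that it fails at the margin of 7. The first ignores a later lock, and the second borrows the wrong SD. The pattern looks like text carried over from a 12-month endpoint, but that is inference.

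The result assumes that funding ends at month 36, that accrual is even within Table 3 columns, that infants are enrolled at about 0-1 month of age, and that all 150 registry infants reach 24 months on schedule. Parts of the document were not available for this review, so an extension stated there cannot be excluded. Table 3 and the six-month sentence would still need correcting.

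**What to change.** Tie the primary data lock and the final analysis to the last 24-month telephone visit, at about month 48. The cost is later reporting, about three months past the month-45 data deadline even before cleaning.

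If the grant end or the data deadline cannot move, state the expected number of infants with a 24-month WIDEA score at the chosen lock. Give the corresponding power or margin for Aim 1a, with the 24-month SD printed, and the Aim 3 detectable difference for the families who will have reached 24 months. This costs only wording, though the figures will be less favourable.

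In either case, delete the sentence about six additional recruitment months and correct the 24-month row for newly enrolled subjects in Table 3. A longitudinal model on the 12-, 18- and 24-month scores, so that later enrolees contribute the visits they have reached, is an option only if the lock comes before the last 24-month visit. It would have to be prespecified.
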